## 7. SAFETY DEFINITIONS, REPORTING, AND MONITORING

### 7.1. Definitions

#### 7.1.1. Adverse Event

An AE is any untoward medical occurrence in a patient administered a study drug which may or may not have a causal relationship with the study drug. Therefore, an AE is any unfavorable and unintended sign (including abnormal laboratory finding), symptom, or disease which is temporally associated with the use of a study drug, whether or not considered related to the study drug.

An AE also includes any worsening (ie, any clinically significant change in frequency and/or intensity) of a preexisting condition that is temporally associated with the use of the study drug.

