4.6. Safety Variables

4.6.1. Adverse Events and Serious Adverse Events Variables

The primary endpoint in the study is the incidence and rate (events per patient-year) of treatment-emergent adverse events (TEAEs) through the last study visit.

The key secondary endpoints related to AE is

- Incidence and rate (events per patient-year) of SAEs and AEs of special interest

Adverse events and serious adverse events will be collected from the time of informed consent signature and then at each visit until the end of the study. All adverse events are to be coded to a “Preferred Term” and associated primary “System Organ Class (SOC)” according to the Medical Dictionary for Regulatory Activities (MedDRA, latest version).

An **Adverse Event** is any untoward medical occurrence in a patient administered a study drug which may or may not have a causal relationship with the study drug. Therefore, an AE is any unfavorable and unintended sign (including abnormal laboratory finding), symptom, or disease which is temporally associated with the use of a study drug, whether or not considered related to the study drug.

AEs also include: any worsening (i.e., any clinically significant change in frequency and/or intensity) of a pre-existing condition that is temporally associated with the use of the study drug; abnormal laboratory findings considered by the investigator to be clinically significant; and any untoward medical occurrence.

A **Serious Adverse Event** is any untoward medical occurrence that at any dose results in death; is life-threatening; requires in-patient hospitalization or prolongation of existing hospitalization; results in persistent or significant disability/ incapacity; is a congenital anomaly/ birth defect; or is an important medical event.

The criteria for determining whether an abnormal laboratory, vital sign or ECG finding should be reported as an AE are as follows:

- Test result is associated with accompanying symptoms, and/or
- Test result requires additional diagnostic testing or medical/surgical intervention, and/or
- Test result leads to a change in dosing (outside of protocol-stipulated dose adjustments) or discontinuation from the study, significant additional concomitant drug treatment, or other therapy

The pre-treatment period is defined as the period from the subject providing informed consent up to the first dose of study drug in current study.

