Hence any AE with an onset between the end of study visit under protocol amendment 6 and the date of first injection under amendment 7; or between end of study visit under protocol amendment 7 and date of first injection under amendment 8 is **not** considered TEAEs.

The list of adverse events of special interest (AESI) was revised several times. Below is the AESI list under protocol amendments 4 and 5:

- Anaphylactic reactions
- Acute allergic reaction
- Severe injection site reactions that last longer than 24 hours
- Mycosis fungoides
- Cutaneous T-cell dyscrasia
- Any severe infection
- Any infection requiring treatment with parenteral antibiotics
- Any infection requiring treatment with oral antibiotics/anti-viral/anti-fungal for longer than 2 weeks
- Any clinical endoparasitosis
- Any opportunistic infection

Under protocol amendment 6, suicide-related events and certain eye-related events were added as AESIs. Under protocol amendment 7, the list of AESI are as follows:

- Anaphylactic reactions
- Systemic or extensive hypersensitivity reactions
- Malignancy (except basal cell carcinoma)
- Helminthic infections
- Any suicide-related events
- Any type of conjunctivitis or blepharitis, or keratitis (severe or serious)

The SAP summarizes AESIs according to the most current list under protocol amendments 7 and 8. The definition of AESI is same under protocol amendment 7 and 8.

[Appendix 10.6](#) provides a list of AESIs search criteria.

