5.11.3. Immunogenicity and Safety and Efficacy

Association of ADA with safety events may be explored with a primary focus on the following safety events during the TEAE period:

- Hypersensitivity (SMQ: Hypersensitivity [Narrow])
- Anaphylaxis (SMQ: Anaphylaxis [Narrow])

Association of treatment emergent and persistent ADA responses and impact on selected efficacy endpoints (ie proportion of patients with IGA 0 or 1, proportion of patients with EASI-75, percent change in EASI score) may be explored (e.g. scatter plot or spaghetti plot).

These above mentioned safety and efficacy analyses will be conducted using the following ADA response categories:

- ADA positive patients, that is patients with treatment-emergent or treatment-boosted response
- ADA negative patients, that is patients with pre-existing immunoreactivity or negative in the ADA assay at all time points
- Patients with persistent ADA response,
- NAb positive patients, that is patients who had positive in the NAb assay at any time point analyzed.
- Peak post-baseline titer level in treatment emergent or treatment boosted ADA positive patients:
 - High,
 - Moderate,
 - Low

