10.6. Search Criteria for TEAE of Special Interest/TEAE Syndrome

Below table is the search criteria for AESI under protocol amendment 4 and 5.

AESI	Search Criteria
Anaphylactic reactions	Narrow SMQ for “anaphylactic reaction”
Acute allergic reactions that require treatment	Narrow SMQ for “hypersensitivity” Action taken for AE=“medication” or “surgery” Note: Blinded manual adjudication of relevant PTs will be required by the study medical monitor, before database locks
Severe ISRs that last longer than 24 hours	-HLT = Injection site reactions - Severity = “severe” - duration of AE > 24 hours
Mycosis fungoides or other forms of cutaneous T cell lymphoma	-HLT = “Mycosis fungoides” • Includes LLT = Sezary syndrome • Includes LLT = Cutaneous T-cell lymphoma -PT = “Cutaneous T-cell dyscrasia
Any severe infection	-SOC = Infections and infestations -Severity = “severe
Any infection requiring treatment with parenteral antibiotics	-SOC = Infection and infestations -Action taken for AE = “medication” -ConMed: ATC3= “Antiinfectives” during the TEAE course (between start and stop dates), Route = IV, IM
Any infection requiring treatment with oral antibiotic/anti-viral/anti-fungal for longer than 2 weeks	-SOC = Infection and infestations -Action taken for AE = “medication” -Check CM: ATC3= “Antiinfectives” during the TEAE course (between start and stop dates), Route = PO and Treatment duration >14 days
Any clinical endoparasitosis	-HLT = Cestode infections -HLT = Helminthic infections NEC -HLT = Nematode infections -HLT = Trematode infection

AESI	Search Criteria

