Any opportunistic infection ^a	The following HLTs plus PTs -HLT = Pneumocystis infection -HLT* = Fungal infections NEC -HLT* = Pseudallescheria infections -HLT = Herpes viral infections -HLT = Paracoccidioides infections -HLT = Sporothrix infections -HLT = Cryptosporidia infections -HLT* = Trypanosomal infections -HLT* = Campylobacter infections -HLT* = Shigella infections -HLT* = Vibrio infections Plus the following PTs -Polyomavirus-associated nephropathy -BK virus infection -Cytomegalovirus infection -Post transplant lymphoproliferative disorder -Progressive multifocal leukoencephalopathy -*Bartonellosis -Blastomycosis -Toxoplasmosis -Coccidioidomycosis -Histoplasmosis -*Aspergillus infection -Systemic candida -Oropharyngeal candidiasis -Cryptococcosis -Listeriosis -Tuberculosis -Nocardiosis -Mycobacterial infection -*Salmonellosis -*Hepatitis B -Herpes zoster -*Strongyloidiasis -Microsporidia infection -Visceral leishmaniasis -*Hepatitis C -Eczema herpeticum

AESI	Search Criteria
	-Kaposi's varicelliform eruption -Herpes zoster Note: *Blinded manual adjudication of relevant PTs under each of HLTs listed above will be required by the study medical monitor, before database locks
Suicidal behavior	Include the following PTs -Completed suicide -Suicidal ideation -Suicide attempt -Depression suicidal -Suicidal behavior

^a The definition of opportunistic infections is referring to the recent consensus guidance for opportunistic infections in the setting of biologic therapy (K L Winthrop et al, 2015)

Below table is the search criteria for AESI under protocol amendment 6/7/8.

AESI	Search Criteria

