Anaphylactic reactions	For SMQ “anaphylactic reaction” An algorithmic approach will be used. A case must include either: 4. A narrow term (a term from Category A); 5. Patient with both a term from Category B AND a term from Category C ; 6. Patient with a term from Category D AND { a term from Category B - OR a term from Category C } For bullets 2 and 3, the search terms that are included under the SMQ for a particular event need to have the same start date (for e.g. if search shows cough (category B term) occurring at day 3 and urticaria (category C term) occurring at day 7, this event is not adjudicated as anaphylactic reaction as this is inconsistent with the clinical presentation of anaphylaxis as an acute event with simultaneous involvement of 2 or more body systems. Note: manual adjudication of relevant PTs will be required by the study medical monitor, before database lock

AESI	Search Criteria
Systemic or severe hypersensitivity reactions	
Hypersensitivity: Narrow SMQ for hypersensitivity excluding preferred term equal to dermatitis atopic or eczema
 
For systemic hypersensitivity, events in which 2 or more body systems are involved (as defined by System Organ Class) would be considered for adjudication based on further medical judgement
 
For severe hypersensitivity, an additional search will be done;
 
 - HLT = Injection site reactions - Severity = “severe” 
Note: manual adjudication of relevant PTs will be required by the study medical monitor, before database lock

Malignancy	
 • SMQ “Malignant tumours” • SMQ “Tumours of unspecified malignancy”
Helminthic infections	
-HLT = Cestode infections
 
-HLT = Helminthic infections NEC
 
-HLT = Nematode infections
 
-HLT = Trematode infection

Suicidal behavior	
Include the following PTs
 
 • Completed suicide • Suicidal ideation • Suicide attempt • Depression suicidal • Suicidal behavior

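### The optional ADA-safety analysis in SAP 5.11.3 counts atopic dermatitis and eczema terms as hypersensitivity, although the current AESI search in SAP 10.6 excludes them from the same SMQ

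*SAP*

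**What the plan says.** SAP 5.11.3 allows, but does not require, an exploration of ADA against two safety events during the TEAE period: hypersensitivity and anaphylaxis. Hypersensitivity is given as "Hypersensitivity (SMQ: Hypersensitivity [Narrow"]). No preferred term (PT) is excluded, and there is no cross-reference to Appendix 10.6. The same section then considers ADA against IGA 0 or 1, EASI-75 and percent change in EASI, using the same ADA response categories.

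SAP 10.6 holds two AESI search tables. The later one is introduced by "Below table is the search criteria for AESI under protocol amendment 6/7/8", and its hypersensitivity row begins with "Narrow SMQ for hypersensitivity excluding preferred term equal to dermatitis atopic or eczema". SAP 4.6.1 makes this the operative table: "The SAP summarizes AESIs according to the most current list under protocol amendments 7 and 8". The earlier table, for amendments 4 and 5, uses "Narrow SMQ for “hypersensitivity" without that exclusion, but restricts it to events that needed treatment and requires adjudication.

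On what counts as an adverse event, Protocol 7.1.1 states that "An AE also includes any worsening" of a preexisting condition, and SAP 4.6.1 repeats this. SAP 4.6.1 also treats every adverse event with onset in the treatment or follow-up period as treatment-emergent.

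**The concern.** Every patient in this study has AD. If the hypersensitivity event includes the PTs to which worsening AD may be coded, the ADA comparison mixes two questions: whether ADA goes with immune reactions to the drug, and whether it goes with poorer disease control. SAP 5.11.3 treats the second as a separate efficacy question. A reader of the report could take a difference in flares for a difference in hypersensitivity, or miss a real hypersensitivity difference under a background of flares. Immunogenicity is a stated secondary objective, and hypersensitivity is one of only two safety events singled out for this exploration.

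**Working it through.** The documents state no figure on this point, so there is nothing to reproduce. The check sets the passages side by side.

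1. **Same starting search.** SAP 5.11.3 and the current row of SAP 10.6 both begin from the narrow hypersensitivity SMQ. At that line they differ by two PTs, dermatitis atopic and eczema.
2. **The two PTs lie within the SMQ.** This is inferred from SAP 10.6: the exclusion would have no purpose otherwise.
3. **Flares reach the analysis.** SAP 4.6.1 counts as an adverse event "any clinically significant change in frequency and/or intensity) of a pre-existing condition" linked in time to study drug. With onset on treatment or in follow-up it is a TEAE. A flare coded to either PT is therefore a hypersensitivity case under 5.11.3 and is removed at the base search line of 10.6.
4. **Nothing corrects it.** No other passage carries the exclusion into 5.11.3. Table 1 in SAP 1.2.4 records that version 2.0 updated both the AESI search (4.6.1, 10.6) and the ADA analysis (5.10, 5.11). It gives no reason for the difference.
5. **The SAP treats a link between ADA and disease control as possible.** SAP 1.1 mentions an impact of ADA on trough concentration and clinical parameters, 5.11.1 explores ADA against exposure, and 5.11.3 explores ADA against efficacy.

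The direction of the effect follows from simple algebra. Let h be the incidence of true hypersensitivity and f the incidence of the two AD terms in ADA-negative patients, independent within ADA group. Let Rh and Rf be the risk ratios for ADA-positive patients. The risk ratio under the untrimmed definition is

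[1 − (1 − h·Rh)(1 − f·Rf)] / [1 − (1 − h)(1 − f)],

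and under the trimmed definition it is Rh.

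The rates below are assumptions chosen only to show direction: h from 1% to 3%, f from 5% to 20%. Worked case with h = 0.03 and f = 0.10; the ADA-negative incidence is 1 − 0.97 × 0.90 = 0.127:

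- **ADA doubles flares only** (Rh = 1, Rf = 2): 1 − 0.97 × 0.80 = 0.224, and 0.224/0.127 = 1.76. Trimmed: 1.00. Range over the assumed rates: 1.62 to 1.95.
- **ADA triples true hypersensitivity only** (Rh = 3, Rf = 1): 1 − 0.91 × 0.90 = 0.181, and 0.181/0.127 = 1.43. Trimmed: 3.00. Range: 1.08 to 1.73.
- **ADA affects neither:** both definitions give 1.00.

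**The case against.** The strongest reply concerns weight. The analysis is optional, it is not a listed endpoint, and SAP section 1 rules out hypothesis testing. Protocol 9.5.5 likewise makes any assessment of ADA impact on safety discretionary. All of this stands, and it is why the severity is low.

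Four stronger readings are tempting and are not supported.

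- **That a false hypersensitivity signal will appear in ADA-positive patients.** The same SMQ applies to ADA-negative patients. A spurious association needs more flare events with ADA; otherwise the effect is only dilution. Nor is every flare captured: it must be reported as an adverse event and coded to one of the two PTs.
- **That a false-positive rate or a loss of power can be quoted.** No test is planned. ADA prevalence, hypersensitivity incidence and AD-term incidence are not in the documents, and any such figure moves widely with the values chosen.
- **That 5.11.3 contradicts the whole AESI definition.** The 10.6 row is for systemic or severe hypersensitivity. It adds involvement of two or more body systems, a search for severe injection site reactions, and a note that "manual adjudication of relevant PTs will be required by the study medical monitor, before database lock". Some difference from a broad SMQ screen is expected. The unexplained part is the two PTs in the shared base search.
- **That the exclusion is already programmed.** The documents show a search specification, not programs.

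One further objection stands in part. A drug-related eczematous reaction could be coded to eczema, so dropping the untrimmed SMQ altogether would lose information. The fix keeps it alongside.

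**Conclusion.** The mismatch is real and the documents do not resolve it. As written, AD flares coded to dermatitis atopic or eczema enter the ADA-hypersensitivity comparison. They dilute a true association and, if ADA worsens AD control, present an efficacy effect as hypersensitivity.

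The size is unknown. The risk ratios above rest on assumed rates and on independence of the two event types, so they show direction only. The conclusion also rests on the inference that the narrow SMQ contains the two PTs. The text mismatch is certain; the amount of distortion is not. Severity is low: the analysis is exploratory and descriptive, and no primary or key secondary endpoint is affected. It is still worth correcting, because the correction is cheap and makes the result interpretable.

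**What to change.** In SAP 5.11.3, define the event as the narrow hypersensitivity SMQ excluding the PTs dermatitis atopic and eczema. This matches the base search line of SAP 10.6 and should be described that way, because it does not bring in the body-system, injection-site-reaction or adjudication elements of the full AESI row. Show the untrimmed SMQ beside it as a sensitivity summary. Tabulate the two PTs by ADA status with the ADA-efficacy results, where a difference in flares belongs.

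The cost is one line of specification and slightly more output, with no new data. The downside is that a drug-related reaction coded to eczema would appear only in the sensitivity summary and the PT table.

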2.3. Study Plan (Schedule of Study Assessment)

The study consists of a screening period, a treatment period and a follow-up period. The dose level, the duration of treatment period and follow-up period were modified for the study through several protocol amendments. These modifications are outlined in [Table 1](#).

Table 2: Study dose level and study duration under each protocol version

Protocol Version	Country	Dose Level (mg)	Duration of Treatment Period	Duration of Follow-up period
Original and amendment 1	Global	200	100 weeks	16 weeks
Amendment 2 and 3	Global	300	100 weeks	16 weeks
Amendment 4	Global	300	148 weeks or until commercially available	16 weeks
Amendment 5 and 6	Great Britain	300	100 weeks	16 weeks
Amendment 6	Global, Hungary, Japan	300	148 weeks or until commercially available	16 weeks
Amendment 7	Global, Hungary	300	148 weeks or until commercially available	12 weeks
Amendment 7*	France, Germany, Poland, Japan	300	Extend treatment period through approximately 31 December 2017	12 weeks
Amendment 7	Great Britain	300	100 weeks	12 weeks
Amendment 8**	Poland, Finland	300	Extend treatment period to up to 5 years (week 260)	12 weeks
Amendment 8**	France	300	Extend treatment period to approximately September 2018	12 weeks

* Note: Under protocol amendment 7 for France, Germany, Poland and Japan, patients who had already completed the End of Treatment visit under protocol amendment 6 were permitted to resume treatment with study drug. Patients who had completed the End of Study visit were permitted to re-enter the study. The treatment period ended for all patients in these countries on or about 31 December 2017.

** Note: Patients in Poland, Finland and France who had completed their End of Treatment/End of Study visit as per amendment 7 were permitted to resume treatment/re-enter the study provided that no more than 12 weeks had elapsed since their End of Study visit. The duration of the overall treatment period for patients in Poland and Finland was extended to 5 years, and to September 2018 for patients in France.

The study flow diagrams under protocol amendment 7 and 8 are provided in [Figure 2](#), [Figure 3](#), [Figure 34](#) and [Figure 35](#) below:

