5.10. Analysis of ADA Data

5.10.1. Analysis of ADA Data

The ADA variables described in Section 4.8 will be summarized using descriptive statistics in the ADA analysis set. Frequency tables of the proportion of patients with pre-existing immunoreactivity, treatment-emergent, treatment-boostered, persistent ADA responses, and titer categories will be presented as absolute occurrence (n) and percent of patients (%).

- Pre-existing immunoreactivity is defined as either an ADA positive response in the assay at baseline of parent study with all ADA results negative post first dose of the current study, OR a positive response at baseline of parent study with all ADA results less than 4-fold baseline titer levels of parent study, post first dose of the current study.
- Treatment emergent response is defined as a positive response in the ADA assay post first dose of current study when baseline results of parent study are negative or missing. The treatment emergent responses will be further characterized as Persistent, Indeterminate or Transient
 - Persistent Response – defined as a treatment emergent ADA response with two or more consecutive ADA positive sampling time points separated by greater than (>) 12-week period (greater than 84 days), with no ADA negative samples in between.
 - Indeterminate Response – defined as a treatment-emergent response with only the last collected sample positive in the ADA assay
 - Transient Response - defined as a treatment emergent ADA positive assay response that is not considered persistent or indeterminate.
- Treatment boostered response is defined as a positive response in the ADA assay post first dose that is greater than or equal to 4-fold over baseline titer levels of parent study, when baselines results of parent study are positive.

The baseline used to define ADA status (treatment emergent, pre-existing immunoreactivity, etc) refers to the baseline ADA value in the parent study.

- Titer Values (Titer value category)
 - Low (titer <1,000)
 - Moderate ($1,000 \leq \text{titer} \leq 10,000$)
 - High (titer >10,000)

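### SAP 5.11.3 relates ever-in-study ADA status to events anywhere in the TEAE period, with no time order and no exposure adjustment by ADA status, so it can create or mask an association

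*SAP*

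**What the plan says.** SAP 5.11.3 makes the analysis optional: "Association of ADA with safety events may be explored with a primary focus on the following safety events during the TEAE period". The two named event groups are the narrow standardised MedDRA queries for hypersensitivity and anaphylaxis. If the analysis is done, the section fixes the categories to be used, all at patient level:

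- **ADA-positive:** "ADA positive patients, that is patients with treatment-emergent or treatment-boosted response". SAP 5.10.1 supplies the first component: "Treatment emergent response is defined as a positive response in the ADA assay post first dose of current study", given a negative or missing parent-study baseline. A boosted response is a titer at least 4-fold over a positive parent-study baseline.
- **ADA-negative:** "ADA negative patients, that is patients with pre-existing immunoreactivity or negative in the ADA assay at all time points".
- **Neutralizing antibody:** "NAb positive patients, that is patients who had positive in the NAb assay at any time point analyzed".
- **Persistent:** a treatment-emergent response with "two or more consecutive ADA positive sampling time points separated by greater than (>) 12-week period" and no negative sample between.
- **Titer:** the post-baseline peak.

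Under SAP 4.6.1, treatment-emergent events are those with onset in the treatment or follow-up periods, starting at the first dose of this study. Only the off-study interval before re-entry under amendments 7 and 8 is excluded.

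SAP Table 2 shows planned treatment of 100 weeks (Great Britain), 148 weeks or until commercial availability (most countries) or up to 260 weeks (Poland and Finland), followed by 12 or 16 weeks off drug. SAP 5.4 acknowledges that duration differs by country.

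SAP 5.8.1 and 10.5 define events per 100 patient-years (NEPY) and patients with an event per 100 patient-years (EAIR) for the overall adverse-event and AESI tables. SAP 5.11.3 does not ask for them by ADA category, and their person-time is not divided at ADA onset. Protocol 9.5.5 says only that the impact of ADA on safety and efficacy may be assessed.

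**The concern.** Every category in SAP 5.11.3 is settled by samples taken up to the end of a patient's stay, while events are counted from the first dose. Two problems follow.

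The first is length of stay. A patient followed longer has more samples that could turn positive and more time to have an event. The ADA-negative group is therefore weighted towards short follow-up. The persistent category depends on length of stay even more, since it needs positives more than 84 days apart.

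The second is time order. A reaction in year 1 counts in the ADA-positive column even if the first positive sample is in year 3. If the event itself shortens follow-up, the error runs the other way: the patient is no longer sampled, cannot become ADA-positive later, and the event is recorded as ADA-negative.

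Immunogenicity on re-treatment is a secondary objective, and SAP 1.1 names its effect on clinical parameters as something the study may inform. A spurious association, or a hidden one for the more serious event, would mislead on that question.

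**Working it through.** The plan states no ADA rate, event rate or expected ratio for this comparison, so there is no figure to reproduce. The check asks what the specified comparison returns when ADA and events are generated independently, so that the correct ratio is 1.

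**From the documents.** The category definitions and event window above. ADA samples at weeks 48, 100, 124, 148, 172, 220 and 260 and at end of study (Protocol 6.2). Anaphylaxis permanently ends dosing (Protocol 5.2.2.1).

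**Assumed.** First-event rate 1 to 10 per 100 patient-years, or 0.5 to 2 where the event ends follow-up. ADA onset rate 2 to 5 per 100 patient-years (5 where the event ends follow-up). ADA permanent or lasting 26 weeks on average. Follow-up patterns as in the table, with 2,000,000 patients per scenario.

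**Measures, ADA-positive over ADA-negative.**

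- Crude ratio: proportion with an event in each group.
- Whole-period EAIR ratio: (patients with an event / sum of time to first event, or of total follow-up if none), by ever-ADA group.
- Time-split ratio: event rate after the first positive sample, over the rate in all earlier time plus all time in ADA-negative patients.

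| Follow-up (weeks) | Event ends follow-up? | Crude | Whole-period EAIR | Time-split |
|---|---|---|---|---|
| 160 for all | no | 0.96–1.01 | 0.96–1.03 (all four rows) | 0.92–1.04 (all four rows) |
| 112/160/272 (30/50/20%) | no | 1.09–1.14 | | |
| Uniform 16–272 | no | 1.24–1.29 | | |
| 52/160/272 (one third each) | no | 1.29–1.36 | | |
| 160 for all | yes | 0.53–0.56 | 0.53–0.55 | 0.96–0.99 |
| Uniform 16–272 | yes | 0.70–0.71 | 0.54–0.55 | 0.96–1.01 |

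**Hand check of the follow-up effect.** In the uniform case mean follow-up is about 181 weeks in ADA-positive and 142 in ADA-negative patients (5 events and 2 ADA onsets per 100 patient-years). Expected proportions are 1 − exp(−0.05 × 181/52) = 0.160 and 1 − exp(−0.05 × 142/52) = 0.128, a ratio of 1.25. The simulation, which uses the full spread of follow-up, gave 0.159 and 0.125, a ratio of 1.27.

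**Time order.** Where the event does not end follow-up, 58 to 68% of ADA-positive patients with an event had it before their first positive sample, and 48 to 61% before true ADA onset. This occurs even with equal follow-up. Where the event ends follow-up, 31 to 40% precede the first positive sample, because an end-of-study sample can still turn positive afterwards.

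**A second follow-up mix.** 20% leave before week 100, 45% end at weeks 60 to 148, 23% at week 148 and 12% at week 260, each plus 12 weeks. With 6 first events per 100 patient-years and about 6% ADA-positive, follow-up was 163 against 133 weeks, the crude ratio 1.21, and 63 to 64% of ADA-positive patients' events came before the first positive sample. The time-split ratio was 1.00, and on this mix so was the EAIR ratio.

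**Sensitivity to ADA timing.** Amendment 6 removed ADA samples at weeks 4, 12, 52, 68, 92 and 116, so patients enrolled before it had earlier samples. Restoring them gave a crude ratio of 1.22 with 59% before the first positive. If ADA appears early (mean 30 weeks), the crude ratio falls to about 1.02 and the share to 32 to 43%.

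**The case against.** **It is optional and descriptive.** The SAP plans no hypothesis test and 5.11.3 names no metric. This stands. A reader might infer an inflated false-positive rate: Fisher's exact test on the crude table would reject in 10 to 33% of null runs at 3 to 12 first events per 100 patient-years, but in only 2 to 6% at 0.05 to 0.3. No such test is in the plan, so those figures are illustrative only.

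**The bias always counts against ADA.** A reader might infer this from the varying follow-up. The documents do not support it. Anaphylaxis ends dosing and so cuts off later sampling, which pushes the ratio below 1.

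**The SAP already has the remedy for follow-up.** Partly right. Where events do not end follow-up, the whole-period EAIR ratio is close to 1. But 5.11.3 does not call for EAIR by ADA category. EAIR also leaves misordered events in place and stays near 0.54 when the event ends follow-up.

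**Many patients may have early or pre-existing ADA.** This stands as a limit on size. Status is judged against the parent-study baseline, so a patient who seroconverted in the parent study enters already positive and has no pre-ADA time here. The simulations start every onset after Day 1 and so overstate the misordered share for such patients.

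**Splitting at the first positive sample can hide a real effect.** This stands. Median detection lag was about 17 weeks on the current schedule. With a true 5-fold effect lasting 12 weeks from onset, the split gave 1.10 to 1.11, whole-period EAIR 1.29 and the crude ratio 1.52. For a lasting effect the split recovered 4.8 of 5.

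**Listings allow case review.** ADA results and adverse events are both to be listed by patient, so timing could be reconstructed. That helps for a few cases but does not correct the summary comparison.

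**Conclusion.** The point holds for the comparison as specified, if it is carried out. Ever-in-study ADA, neutralizing-antibody, persistent and peak-titer categories are set against events from any part of the TEAE period, with no rule on time order and no exposure adjustment by ADA status. With no true association, the crude ratio can be about 1.1 to 1.4 when follow-up varies and about 0.5 to 0.7 when the event ends follow-up. Roughly 60% of ADA-positive patients' events precede the first positive sample where events do not end follow-up, and fewer if ADA appears early or was present at entry.

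These sizes rest on assumed event rates, ADA rates and follow-up mixes. The mechanism rests only on the SAP's definitions. The documents do not show that an observed association would be an artefact, only that this comparison could not tell. The primary safety endpoint is unaffected. The change is worth making because it is cheap and concerns a secondary objective.

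**What to change.** Amend SAP 5.11.3, or the future addendum that SAP section 7 foresees, as follows:

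1. Report NEPY and EAIR (SAP 10.5) by ADA category, not crude proportions alone.
2. Add an analysis with ADA as a time-dependent status. Events and person-time count as ADA-positive only after the first positive or boosted sample, or from Day 1 if the patient was already positive at entry. All earlier time, and all time in ADA-negative patients, counts as ADA-negative.
3. Add a sensitivity analysis that starts ADA-positive time at the last negative sample, since onset is known only to lie between two samples. It uses a later result to classify earlier time, so read it as a bound.
4. List each hypersensitivity or anaphylaxis event with its timing relative to the last negative and first positive samples.
5. Keep the ever-ADA grouping as supportive.

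The cost is SAP wording and two derived dates per patient from samples already collected. Few events will fall in ADA-positive time, so estimates will be imprecise. Splitting at first detection can dilute a short-lived effect near onset, which is why items 1 and 3 should be shown beside item 2.
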